## 6.2 Assessing and Recording Adverse Events

An adverse event is defined as any untoward medical occurrence in a patient or clinical investigation subject administered a pharmaceutical product and which does not necessarily have to have a causal relationship with this treatment. An adverse event can therefore be any unfavorable and unintended sign (including an abnormal laboratory finding, for example), symptom, or disease temporally associated with the use of a medicinal product or protocol-specified procedure, whether or not considered related to the medicinal product or protocol-specified procedure. Any worsening (i.e., any clinically significant adverse change in frequency and/or intensity) of a preexisting condition that is temporally associated with the use of the Merck's product, is also an adverse event.

Changes resulting from normal growth and development that do not vary significantly in frequency or severity from expected levels are not to be considered adverse events. Examples of this may include, but are not limited to, teething, typical crying in infants and children and onset of menses or menopause occurring at a physiologically appropriate time.

Merck product includes any pharmaceutical product, biological product, device, diagnostic agent or protocol-specified procedure, whether investigational (including placebo or active comparator medication) or marketed, manufactured by, licensed by, provided by or distributed by Merck for human use.

Adverse events may occur during the course of the use of Merck product in clinical trials or within the follow-up period specified by the protocol, or prescribed in clinical practice, from overdose (whether accidental or intentional), from abuse and from withdrawal.

Adverse events may also occur in screened subjects during any pre-allocation baseline period as a result of a protocol-specified intervention, including washout or discontinuation of usual therapy, diet, placebo treatment or a procedure.

Progression of the cancer under study is not considered an adverse event unless it is considered to be drug related by the investigator.

In addition to documenting all Grade 3 or higher toxicities during radiation therapy, all adverse events will be recorded from the time of study intervention (pembrolizumab) through 30 days following cessation of treatment and at each examination on the Adverse Event case report forms/worksheets. The reporting timeframe for adverse events meeting any serious criteria is described in section 7.2.3.1.

## **6.2.1 Definition of an Overdose for This Protocol and Reporting of Overdose to the Sponsor and to Merck**

For purposes of this trial, an overdose of pembrolizumab will be defined as any dose of 1,000 mg or greater ( $\geq 5$  times the indicated dose). No specific information is available on the treatment of overdose of pembrolizumab. Appropriate supportive treatment should be provided if clinically indicated. In the event of overdose, the subject should be observed closely for signs of toxicity. Appropriate supportive treatment should be provided if clinically indicated.

If an adverse event(s) is associated with (“results from”) the overdose of a Merck product, the adverse event(s) is reported as a serious adverse event, even if no other seriousness criteria are met.

If a dose of Merck’s product meeting the protocol definition of overdose is taken without any associated clinical symptoms or abnormal laboratory results, the overdose is reported as a non-serious Event of Clinical Interest (ECI), using the terminology “accidental or intentional overdose without adverse effect.”

All reports of overdose with and without an adverse event must be reported within 24 hours to the Sponsor and within 2 working days to Merck Global Safety. (Attn: Worldwide Product Safety; [contact]).

## 6.2.2 Reporting of Pregnancy and Lactation to the Sponsor and to Merck

Although pregnancy and lactation are not considered adverse events, it is the responsibility of investigators or their designees to report any pregnancy or lactation in a subject (spontaneously reported to them), including the pregnancy of a male subject's female partner that occurs during the trial or within 120 days of completing the trial completing the trial, or 30 days following cessation of treatment if the subject initiates new anticancer therapy, whichever is earlier. All subjects and female partners of male subjects who become pregnant must be followed to the completion/termination of the pregnancy. Pregnancy outcomes of spontaneous abortion, missed abortion, benign hydatidiform mole, blighted ovum, fetal death, intrauterine death, miscarriage and stillbirth must be reported as serious events (Important Medical Events). If the pregnancy continues to term, the outcome (health of infant) must also be reported.

Such events must be reported within 24 hours to the Sponsor and within 2 working days to Merck Global Safety. (Attn: Worldwide Product Safety; [contact])

## 6.2.3 Immediate Reporting of Adverse Events to the Sponsor and to Merck

### 6.2.3.1 Serious Adverse Events

#### Serious Adverse Event Reporting (SAE)

An adverse event or suspected adverse reaction is considered "serious" if, in the view of either the investigator or the sponsor, it results in any of the following outcomes:

- Death
- A life-threatening adverse drug experience – any adverse experience that places the patient, in the view of the initial reporter, at immediate risk of death from the adverse experience as it occurred. It does not include an adverse experience that, had it occurred in a more severe form, might have caused death.
- Inpatient hospitalization or prolongation of existing hospitalization
- A persistent or significant incapacity or substantial disruption of the ability to conduct normal life functions.
- A congenital anomaly/birth defect.

Important medical events that may not result in death, be life threatening, or require hospitalization may be considered a serious adverse drug experience when, based upon appropriate medical judgment, they may jeopardize the patient or subject and may require medical or surgical intervention to prevent one of the outcomes listed in this definition. Examples of such medical events include allergic bronchospasm requiring intensive treatment in an emergency room or at home, blood dyscrasias or convulsions that do not result in inpatient hospitalization, or the development of drug dependency or drug abuse (21 CFR 312.32).

- Important medical events as defined above, may also be considered serious adverse events. Any important medical event can and should be reported as an SAE if deemed appropriate by the Principal Investigator or the IND Sponsor, IND Office.**

- All events occurring during the conduct of a protocol and meeting the definition of a SAE must be reported to the IRB in accordance with the timeframes and procedures outlined in "The University of Texas M. D. Anderson Cancer Center Institutional Review Board Policy for Investigators on Reporting Unanticipated Adverse Events for Drugs and Devices". Unless stated otherwise in the protocol, all SAEs, expected or unexpected, must be reported to the IND Office, regardless of attribution (within 5 working days of knowledge of the event).
- All life-threatening or fatal events**, that are unexpected, and related to the study drug, must have a written report submitted within **24 hours** (next working day) of knowledge of the event to the Safety Project Manager in the IND Office.
- Unless otherwise noted, the electronic SAE application (eSAE) will be utilized for safety reporting to the IND Office and MDACC IRB.**
- Serious adverse events will be captured from the time of the first protocol-specific intervention, until 90 days after the last study treatment/intervention, unless the participant withdraws consent. Serious adverse events must be followed until clinical recovery is complete and laboratory tests have returned to baseline, progression of the event has stabilized, or there has been acceptable resolution of the event.**
- Additionally, any serious adverse events that occur after the 30 day time period that are related to the study treatment must be reported to the IND Office. This may include the development of a secondary malignancy.**

#### Reporting to FDA:

- Serious adverse events will be forwarded to FDA by the IND Sponsor (Safety Project Manager IND Office) according to 21 CFR 312.32.

**It is the responsibility of the PI and the research team to ensure that serious adverse events are reported according to the Code of Federal Regulations, Good Clinical Practices, the protocol guidelines, the sponsor's guidelines, and Institutional Review Board policy.**

#### Investigator Communication with Supporting Companies:

Any serious adverse event, or follow up to a serious adverse event, including death due to any cause other than progression of the cancer under study that occurs to any subject from the time of first protocol intervention through 90 days following cessation of treatment, or the initiation of new anti-cancer therapy, whichever is earlier, whether or not related to Merck product, must be reported within 24 hours to the Sponsor and within 2 working days to Merck Global Safety. The MD Anderson Internal SAE Report Form for Prompt Reporting will be used, with the Merck protocol number referenced (3475-360).

Non-serious Events of Clinical Interest will be forwarded to Merck Global Safety and will be handled in the same manner as SAEs.

Additionally, any serious adverse event, considered by an investigator who is a qualified physician to be related to Merck product that is brought to the attention of the investigator at any time outside of the time period specified in the previous paragraph also must be reported immediately to the Sponsor and to Merck.

**SAE reports and any other relevant safety information are to be forwarded to the Merck Global Safety [contact]**

A copy of all 15 Day Reports and Annual Progress Reports is submitted as required by FDA, European Union (EU), Pharmaceutical and Medical Devices agency (PMDA) or other local regulators. Investigators will cross reference this submission according to local regulations to the Merck Investigational Compound Number (IND, CSA, etc.) at the time of submission. Additionally investigators will submit a copy of these reports to Merck & Co., Inc. (Attn: Worldwide Product Safety; [contact]) at the time of submission to FDA.

All subjects with serious adverse events must be followed up for outcome.

### 6.2.3.2 Events of Clinical Interest

Selected non-serious and serious adverse events are also known as Events of Clinical Interest (ECI) and must be recorded as such on the Adverse Event case report forms/worksheets and reported within 24 hours to the Sponsor and within 2 working days to Merck Global Safety. (Attn: Worldwide Product Safety; [contact])Events of clinical interest for this trial include:

1. an overdose of Merck product, as defined in Section 7.2.1 - Definition of an Overdose for This Protocol and Reporting of Overdose to the Sponsor, that is not associated with clinical symptoms or abnormal laboratory results.
2. an elevated AST or ALT lab value that is greater than or equal to 3X the upper limit of normal and an elevated total bilirubin lab value that is greater than or equal to 2X the upper limit of normal and, at the same time, an alkaline phosphatase lab value that is less than 2X the upper limit of normal, as determined by way of protocol-specified laboratory testing or unscheduled laboratory testing.\*

**\*Note:** These criteria are based upon available regulatory guidance documents. The purpose of the criteria is to specify a threshold of abnormal hepatic tests that may require an additional evaluation for an underlying etiology. The trial site guidance for assessment and follow up of these criteria can be found in the Investigator Trial File Binder (or equivalent).

#### 1. Additional adverse events:

A separate guidance document has been provided entitled “Event of Clinical Interest Guidance Document” (previously entitled, “Event of Clinical Interest and Immune-Related Adverse Event Guidance Document”). This document can be found in Appendix 4 and provides guidance regarding identification, evaluation and management of ECIs and irAEs.

ECIs (both non-serious and serious adverse events) identified in this guidance document from the date of first dose through 90 days following cessation of treatment, or 30 days after the initiation of a new anticancer therapy, whichever is earlier, need to be reported within 24 hours to the Sponsor and within 2 working days to Merck Global Safety. (Attn:

Worldwide Product Safety; [contact]), regardless of attribution to study treatment, consistent with standard SAE reporting guidelines.

Subjects should be assessed for possible ECIs prior to each dose. Lab results should be evaluated and subjects should be asked for signs and symptoms suggestive of an immune-related event. Subjects who develop an ECI thought to be immune-related should have additional testing to rule out other etiologic causes. If lab results or symptoms indicate a possible immune-related ECI, then additional testing should be performed to rule out other etiologic causes. If no other cause is found, then it is assumed to be immune-related.

#### **6.2.4 Evaluating Adverse Events**

An investigator who is a qualified physician will evaluate all adverse events according to the NCI Common Terminology for Adverse Events (CTCAE), version 4.0. Any adverse event which changes CTCAE grade over the course of a given episode will have each change of grade recorded on the adverse event case report forms/worksheets.

All adverse events regardless of CTCAE grade must also be evaluated for seriousness.

Table 6 Evaluating Adverse Events

An investigator who is a qualified physician, will evaluate all adverse events as to:

V4.0 CTCAE Grading	Grade 1	Mild; asymptomatic or mild symptoms; clinical or diagnostic observations only; intervention not indicated.
	Grade 2	Moderate; minimal, local or noninvasive intervention indicated; limiting age-appropriate instrumental ADL.
	Grade 3	Severe or medically significant but not immediately life-threatening; hospitalization or prolongation of hospitalization indicated; disabling; limiting self-care ADL.
	Grade 4	Life threatening consequences; urgent intervention indicated.
	Grade 5	Death related to AE
Seriousness	A serious adverse event is any adverse event occurring at any dose or during any use of Merck product that:	
	†Results in death; or	
	†Is life threatening; or places the subject, in the view of the investigator, at immediate risk of death from the event as it occurred (Note: This does not include an adverse event that, had it occurred in a more severe form, might have caused death.); or	
	†Results in a persistent or significant disability/incapacity (substantial disruption of one's ability to conduct normal life functions); or	
	†Results in or prolongs an existing inpatient hospitalization (hospitalization is defined as an inpatient admission, regardless of length of stay, even if the hospitalization is a precautionary measure for continued observation. (Note: Hospitalization [including hospitalization for an elective procedure] for a preexisting condition which has not worsened does not constitute a serious adverse event.); or	
	†Is a congenital anomaly/birth defect (in offspring of subject taking the product regardless of time to diagnosis); or	
	Is a new cancer; (that is not a condition of the study) or	
	Is an overdose (whether accidental or intentional). Any adverse event associated with an overdose is considered a serious adverse event. An overdose that is not associated with an adverse event is considered a non-serious event of clinical interest and must be reported within 24 hours.	
	Other important medical events that may not result in death, not be life threatening, or not require hospitalization may be considered a serious adverse event when, based upon appropriate medical judgment, the event may jeopardize the subject and may require medical or surgical intervention to prevent one of the outcomes listed previously (designated above by a †).	
Duration	Record the start and stop dates of the adverse event. If less than 1 day, indicate the appropriate length of time and units	
Action taken	Did the adverse event cause the Merck product to be discontinued?	
Relationship to test drug	Did the Merck product cause the adverse event? The determination of the likelihood that the Merck product caused the adverse event will be provided by an investigator who is a qualified physician. The investigator's signed/dated initials on the source document or worksheet that supports the causality noted on the AE form, ensures that a medically qualified assessment of causality was done. This initialed document must be retained for the required regulatory time frame. The criteria below are intended as reference guidelines to assist the investigator in assessing the likelihood of a relationship between the test drug and the adverse event based upon the available information.	
	The following components are to be used to assess the relationship between the Merck product and the AE; the greater the correlation with the components and their respective elements (in number and/or intensity), the more likely the Merck product caused the adverse event (AE):	
	Exposure	Is there evidence that the subject was actually exposed to the Merck product such as: reliable history, acceptable compliance assessment (pill count, diary, etc.), expected pharmacologic effect, or measurement of drug/metabolite in bodily specimen?
	Time Course	Did the AE follow in a reasonable temporal sequence from administration of the Merck product? Is the time of onset of the AE compatible with a drug-induced effect (applies to trials with investigational medicinal product)?
	Likely Cause	Is the AE not reasonably explained by another etiology such as underlying disease, other drug(s)/vaccine(s), or other host or environmental factors

Relationship to Merck product (continued)	The following components are to be used to assess the relationship between the test drug and the AE: (continued)	
	Dechallenge	Was the Merck product discontinued or dose/exposure/frequency reduced? If yes, did the AE resolve or improve? If yes, this is a positive dechallenge. If no, this is a negative dechallenge. (Note: This criterion is not applicable if: (1) the AE resulted in death or permanent disability; (2) the AE resolved/improved despite continuation of the Merck product; or (3) the trial is a single-dose drug trial); or (4) Merck product(s) is/are only used one time.)
Rechallenge	Was the subject re-exposed to the Merck product in this study? If yes, did the AE recur or worsen? If yes, this is a positive rechallenge. If no, this is a negative rechallenge. (Note: This criterion is not applicable if: (1) the initial AE resulted in death or permanent disability, or (2) the trial is a single-dose drug trial); or (3) Merck product(s) is/are used only one time). NOTE: IF A RECHALLENGE IS PLANNED FOR AN ADVERSE EVENT WHICH WAS SERIOUS AND WHICH MAY HAVE BEEN CAUSED BY THE MERCK PRODUCT, OR IF REEXPOSURE TO THE MERCK PRODUCT POSES ADDITIONAL POTENTIAL SIGNIFICANT RISK TO THE SUBJECT, THEN THE RECHALLENGE MUST BE APPROVED IN ADVANCE BY THE U.S. CLINICAL MONITOR AS PER DOSE MODIFICATION GUIDELINES IN THE PROTOCOL.	
		The assessment of relationship will be reported on the case report forms /worksheets by an investigator who is a qualified physician according to his/her best clinical judgment, including consideration of the above elements.
Record one of the following		Use the following scale of criteria as guidance (not all criteria must be present to be indicative of a Merck product relationship).
Yes, there is a reasonable possibility of Merck product relationship.	There is evidence of exposure to the Merck product. The temporal sequence of the AE onset relative to the administration of the Merck product is reasonable. The AE is more likely explained by the Merck product than by another cause.	
No, there is not a reasonable possibility Merck product relationship	Subject did not receive the Merck product OR temporal sequence of the AE onset relative to administration of the Merck product is not reasonable OR there is another obvious cause of the AE. (Also entered for a subject with overdose without an associated AE.)	

### **6.2.5 Sponsor Responsibility for Reporting Adverse Events**

All Adverse Events will be reported to regulatory authorities, IRB/IECs and investigators in accordance with all applicable global laws and regulations.

## **7.0 STATISTICAL ANALYSIS PLAN**

### **7.1 Statistical Analysis Plan Summary**

Our Phase I study, consisting of two distinct cohorts of patient, will assess toxicity of two radiation treatment plans. Patients will be assigned to one of two study cohorts based on eligibility characteristics. Randomization is not possible due to the distinct criteria required for the administration of the radiation treatment plan. Each study cohort will be monitored for toxicity independently using a single treatment plan.

### **7.2 Statistical Analysis Plan**

We will enroll a total of 24 patients, twelve patients to each cohort consisting of distinct radiation and immunotherapy treatment plans. For each study cohort, treatment-related toxicity is defined in Table 3 above (in the column “Discontinue Treatment/Off-Study Criteria”. Therefore, any patient meeting this criteria will be deemed to have experienced an “unacceptable” toxicity for the purposes of the trial. For each study condition, we plan to enroll 12 patients in cohorts of size 6. All patients will be monitored for at least 4 months from the beginning of RT, before declaring the treatment acceptable for enrolling the next cohort of 6 patients.

Continuous monitoring using the method of Thall [20] will be employed for each study cohort of 12 patients in cohorts of size 6 where each patient is monitored for at least 4 months from the start of RT. We will stop the trial if we have reason to believe that the treatment-related toxicity rate is more than 30%. Using the following probability rule

$$\Pr(\text{rate of treatment-related toxicity 4 months from the start of RT} > 30\% \mid \text{data}) > 0.80.$$

If we determine there is more than a 80% chance that the treatment-related toxicity rate is more than 30%, we will stop the trial. We will assume a beta(0.6, 1.4) distribution for treatment-related toxicity as this prior provides a mean of 30% and a standard deviation of 26.5%. Thus the trial will be stopped if

$$[\# \text{ of patients with treatment-related toxicity 4 months from day 1 of the start of RT} / \# \text{ of patients evaluated}]$$

$$\geq 3/6, 6/12$$

Therefore, we will stop either study cohort if we observe 3 or more treatment-related toxicities in the first 6 patients, or if we observe 6 treatment related toxicities at any time while evaluating all 12 patients. We will suspend accrual while evaluating the first 6 patients to ensure none of

the stopping boundaries have been reached prior to enrolling the final 6 patients of each study cohort. The operating characteristics from this decision rule are shown in Table X and are based on 1000 simulations for each scenario.

Table X. Operating characteristics for toxicity monitoring rule

Treatment-related Toxicity 4 months after start of RX	Probability of Stopping Early	Sample Size Avg
0.10	0.017	11.9
0.20	0.099	11.4
0.30	0.254	10.5
0.40	0.462	9.2
0.50	0.650	8.1

- Operating Characteristics acquired using the Stata command stopbound

If the true toxicity rate is 0.50, there is a 65.0% probability of stopping the trial early.

Descriptive statistics will be used to summarize the study data. For each study cohort, we will tabulate toxicities by dose, severity, and relationship to the treatment plan. The method of Kaplan and Meier will be used to estimate median PFS and OS.

A Toxicity/Efficacy Summary will be submitted to the IND Medical Monitor after the first 6 evaluable subjects per cohort, complete 4 months from the initiation of Radiation Therapy and prior to the enrollment of the next cohort, and following the treatment of the next 6 evaluable subjects to each cohort.

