**Additional Inclusion Criteria – Cohort 2**

1. Patients must be assessed to be a suitable candidate for radiation therapy by the treating radiation oncologist. Patients that do not meet the dose constraints outlined below will be removed from the study prior to radiation therapy.
2. Any prior number of prior therapies, including prior immunotherapy, is allowed.

3. Patient has received prior treatment with a platinum-pemetrexed regimen.

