### **6.1.4 Other Procedures**

#### **6.1.4.1 Withdrawal/Discontinuation**

**Off-Study Criteria.** Patients will remain on study until completion until they: 1) experience a Grade 3 or higher toxicity during radiation therapy (in which case they will be deemed to be non-evaluable), 2) meet the criteria of Permanent Discontinuation/Off-Study Criteria outlined in Table 3 above (evaluable patient), in which case subjects will be followed until **resolution of symptoms**, 3) are lost-to follow-up, 4) elect to come off study, or 5) die.

When a subject discontinues/withdraws prior to trial completion, all applicable activities scheduled for the final trial visit should be performed at the time of discontinuation. Any adverse events which are present at the time of discontinuation/withdrawal should be followed in accordance with the safety requirements outlined in Section 7.2 - Assessing and Recording Adverse Events. Subjects who a) attain a CR or b) complete 24 months of treatment with pembrolizumab may discontinue treatment with the option of restarting treatment if they meet the criteria specified in Section 7.1.5.5. After discontinuing treatment following assessment of CR, these subjects should return to the site for a Safety Follow-up Visit (described in Section 7.1.5.3.1) and then proceed to the Follow-Up Period of the study (described in Section 7.1.5.4).

If a patient comes off study for toxicity, follow-up will still occur through the research team +/- clinical staff for survival purposes, either through clinic visits as clinically warranted or direct patient calls if the patient no longer follows up at our institution.

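### If a cohort ends with fewer than 12 evaluable patients, the fixed count of 6 toxicities no longer matches the plan's own 0.80 stopping criterion, and no boundary is given for that case

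*Combined protocol and SAP*

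**What the plan says.** Section 7.2 sets the size in enrolled patients: "We will enroll a total of 24 patients, twelve patients to each cohort consisting of distinct radiation and immunotherapy treatment plans". It adds that, for each condition, "we plan to enroll 12 patients in cohorts of size 6". The stopping criterion is a posterior probability above 0.80 that the 4-month treatment-related toxicity rate exceeds 30%, with a beta(0.6, 1.4) prior. The section then prints boundaries of 3/6 and 6/12, with patients evaluated as the denominator. In words, a cohort stops at 3 or more toxicities in the first 6 patients, "or if we observe 6 treatment related toxicities at any time while evaluating all 12 patients".

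The end of 7.2 counts differently: "A Toxicity/Efficacy Summary will be submitted to the IND Medical Monitor after the first 6 evaluable subjects per cohort" complete 4 months, and again "following the treatment of the next 6 evaluable subjects to each cohort".

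Elsewhere, enrolled patients can leave that count:

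- The additional inclusion criteria for Cohort 2, with the same sentence for Cohort 1, state: "Patients that do not meet the dose constraints outlined below will be removed from the study prior to radiation therapy".
- Section 6.1.4.1 takes patients off study for Grade 3 or higher toxicity during radiation, "in which case they will be deemed to be non-evaluable".
- The same section lists loss to follow-up, withdrawal and death as off-study reasons, without saying whether such patients are evaluable.

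There is no replacement rule, no allowance for loss, and no boundary for a final denominator other than 12.

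**The concern.** Twelve enrolled patients give 12 evaluable patients only if none is lost. If a cohort ends with 8 to 11 evaluable, the operational sentence still asks for 6 toxicities. A fixed count over a smaller denominator demands a higher observed rate than the model does, so the mismatch is in the unsafe direction.

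Toxicity is the primary endpoint, and section 4.4.1.2 says the trial is meant to show whether the combination should be explored further in neither population, only the less aggressively treated one, or both. At stake is a cohort that meets the plan's stated probability criterion and yet could be read as acceptable on the printed count.

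**Working it through.** **Inputs.** From 7.2: prior beta(0.6, 1.4), limit 0.30, cut-off 0.80, boundaries 3/6 and 6/12, and the Table X operating characteristics. The loss rate q is an assumption, shown as a range.

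**1. Reproducing the plan.** After x toxicities in n evaluable patients, the posterior is beta(0.6 + x, 1.4 + n − x), and the criterion is its tail above 0.30.

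- 2/6 gives 0.523 and 3/6 gives 0.800003, which only just exceeds 0.80.
- 5/12 gives 0.772 and 6/12 gives 0.905.

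So 3/6 and 6/12 are correct. The Table X probabilities match P(X ≥ 3 of 6): 0.016, 0.099, 0.256, 0.456 and 0.656 at rates 0.1 to 0.5, against the printed 0.017, 0.099, 0.254, 0.462 and 0.650. The differences are within the error of 1000 simulations. Table X therefore describes the first look only.

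**2. Chance of 12 evaluable.** (1 − q)^12 is 0.785, 0.540, 0.282, 0.142 and 0.069 at q = 2, 5, 10, 15 and 20%. It falls below one half when q exceeds 1 − 0.5^(1/12) = 5.6%.

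**3. The same criterion at smaller final n.**

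| Evaluable | Highest count that continues | Lowest count that stops |
|---|---|---|
| 8 | 3 (0.631) | 4 (0.846) |
| 9 | 4 (0.782) | 5 (0.922) |
| 10 | 4 (0.711) | 5 (0.880) |
| 11 | 4 (0.638) | 5 (0.829) |
| 12 | 5 (0.772) | 6 (0.905) |

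A cohort that passes the first look has at most 2 toxicities. With 9 evaluable it can reach at most 2 + 3 = 5, so with 9 or fewer the count of 6 can never be met. With 7 evaluable the model boundary is 4, but such a cohort can reach only 2 + 1 = 3, so no entry is needed there.

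**4. Effect on triggering.** Let n be the final evaluable number, K the final count and p the true rate. Then

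P(trigger) = P(X6 ≥ 3) + Σ(x = 0 to 2) P(X6 = x) · P(X(n−6) ≥ K − x).

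At n = 11 and p = 0.50:

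- K = 6: 0.6562 + 0.09375 × 0.03125 + 0.234375 × 0.1875 = 0.703.
- K = 5: 0.6562 + 0.015625 × 0.03125 + 0.09375 × 0.1875 + 0.234375 × 0.5 = 0.792.

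| n | p = 0.30: count 6 / posterior boundary | p = 0.40: count 6 / posterior boundary | p = 0.50: count 6 / posterior boundary |
|---|---|---|---|
| 10 | 25.8% / 28.5% | 46.4% / 51.6% | 67.1% / 73.5% |
| 11 | 26.6% / 31.8% | 48.5% / 57.1% | 70.3% / 79.2% |
| 12 | 28.2% (same) | 51.9% (same) | 74.7% (same) |

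At rates of 0.40 to 0.50 with 10 or 11 evaluable, the gap between the two boundaries is 5 to 9 percentage points.

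**The case against.** The strongest reply is that the probability statement is the rule and the counts are only its consequence at 6 and 12. Applied directly, it stops 5/10 and 5/11. The boundary is also printed as a ratio over patients evaluated, and 5/10 equals 6/12. This stands in part: a reader might infer that a 5/10 or 5/11 cohort will be passed, and the text does not settle that. But the operational sentence uses a count, and the ratio reading still passes 5/11 (0.455, below 0.50) although the posterior is 0.829.

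Second, the references to 6 and then the next 6 evaluable subjects can be read as accrual until 12 are evaluable, and patients removed for dose constraints before radiation can be read as screen failures. Both readings are possible. Neither is written, and replacing patients who already count as enrolled would conflict with a total of 24.

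Third, a reader might infer that 12 evaluable patients are unlikely. The documents give no loss rate, and at 2% loss the chance is 78.5%. Early deaths do not settle it, because 6.1.4.1 does not call patients who die non-evaluable, and the 9–17 month median survival quoted in section 4.1 is for mesothelioma generally, whereas this trial requires performance status 0 or 1.

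Fourth, a reader might extend the point to median PFS and OS. Section 7.2 plans plain Kaplan-Meier estimates with no evaluability condition, so the point does not reach them.

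**Conclusion.** The point holds as an unreconciled unit (enrolled against evaluable) together with a missing boundary below 12. The printed 3/6 and 6/12 are correct. Where fewer than 12 are evaluable, the count of 6 departs from the plan's own criterion on the lenient side at 4/8, 5/9, 5/10 and 5/11.

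The consequence is limited. Accrual is complete by the final assessment, so what changes is the conclusion about acceptability, not the halting of enrolment. The comparison in the working is conditional on a given number evaluable, assumes that the first look uses 6 evaluable patients, and takes loss as unrelated to toxicity. How often the case arises depends on a loss rate the documents do not state. It should be corrected before the final assessment of either cohort.

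**What to change.** In 7.2:

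- State that 6 and 12 are evaluable patients, define evaluable, and reconcile this with 24 enrolled, either by a replacement rule with a restated total or by keeping 24 as a cap. The definition must also reconcile 6.1.4.1 with the last row of Table 3, since the first makes Grade 3 or higher toxicity during radiation non-evaluable and the second makes Grade 3 or greater radiation-related toxicity an off-study event.
- State that the posterior rule governs when the final evaluable number is below 12, with boundaries 4/8, 5/9, 5/10, 5/11 and 6/12 from the existing prior and cut-off.
- Keep the 3/6 look and the provision to stop at 6 toxicities at any time.
- If the cap of 24 stays, restate the operating characteristics for fewer than 12 evaluable.

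The cost is wording and a five-entry table, with no extra patients under the cap; a replacement rule would raise enrolment. The downside should be disclosed: a cohort with 10 or 11 evaluable can fail at 5 toxicities, and at a true rate of 30% with 11 evaluable, triggering rises from 26.6% to 31.8%, against 28.2% with the full 12.
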